#### DATA QUALITY AND DATA VALIDATION:

Data will be validated for each variable using chart reviews, blood workup or hospital reports to ensure accuracy regularly (at least every 3 month). Data checkup will be conducted yearly by choosing random sample of participants, comparing data with patient chart and measuring percentage of missing data.

#### DATA STORAGE AND MANAGEMENT:

All patients data will be collected from the clinics through our research coordinator and then transferred to unique patient file that will be labeled by patient study number. Data will be entered in data manager program (KSU based – CASIS) through a collaboration with college of medicine research center-clinical research support unite. The primary investigator will have the key for patient identification. In the absence

of the primary investigator, data management will be transferred to KSU-CASIS database manager until a new Investigator is recruited or decision about study termination is taken by the coinvestigator.

#### DATA AND AUTHORSHIP RIGHTS:

All patient data is governed by protocol committee. This committee is consistent of principle investigator and co-investigators. Each member is entitled for his own patients' information (clinical and biological stored samples), however for all cohorts participants, data retrieval will be granted by the committee once study proposal is submitted and reviewed. A primary investigator vote along with one more coinvestigator votes will be required for data to be retrieved. Turnover for study review and approval is two weeks. Principle investigator will be required to choose a successor if he decided to leave the institute.

#### GLOSSARY DEFINITIONS:

Please see the attached appendix for definition of variables in data collection form.

#### BIOLOGICAL SAMPLES AND BIOBANKING PROCESS:

Each patient will have two comprehensive visit during which 4 heparin blood tubes will be collected from the patient for biobanking storage (exception will be for pregnant ~~SLE~~ patients who will have biological sample collection at the beginning of each trimester along with postpartum sample (six weeks from delivery). Once the blood is withdrawn, it will be sorted into: plasma separation, (immune cell sorting using flow cytometry to into major cell line including T-cells, B cells, mononuclear cells and granulocytes/versus storage as PBMC – the decision will be guided by available fund), RNA and DNA then stored at appropriate temperature using patient unique research identification number.

For DNA processing; blood will be collected using standardized phlebotomy technique directly into PAXgene Blood DNA tubes. Sample will be processed in 24 hour in the collaborated lab using PAXgene Blood DNA Kit (please refer to the DNA purification protocol in appendix). After completion of purification step, DNA will be stored in -80 until further utilization. Note that labels with patient study number will be written on the tubes and entered in data management program with location and time of processing in addition to storage location.

For RNA processing; blood will be collected using standardized phlebotomy technique directly into PAXgene Blood RNA Tube. The sample will be then stored in -20 until further utilization in future projects. PAXgene RNA kit will be used to purify RNA and then analysis will be carried using RT-PCR.

For plasma processing; blood will be collected using standardized phlebotomy technique directly into EDTA tube, sample will be centrifuged and buffy coat will be isolated, washed and stored as PBMC while remaining plasma will be transferred to cryovials to be stored into -80 until further use.

Please note that total amount of blood is 5 EDTA tubes that will be collected from the patient in the two visits, two will be used for routine clinical work and rest will be utilized for biobanking as detailed above.

In addition, microbiome data will be collected and stored using RNALater. Patient self-collected fecal samples will be stabilized in RNALater supplied container which contains RNA and DNA stabilizers.

Material will be mixed and allocated in several aliquots that will be stored in -80 until further use.

Sample processing will be handled in collaboration with prince Nayef immunology lab and CMRC core lab facility in complete adherence with standard operational procedure that include sample labelling using patient study number and date collection and processing. Once college of medicine biobank open, all samples will be transferred there for storage and future handling. Sample location, date of separation will be recorded by research coordinator in the data management program.

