## OBJECTIVES

The objectives of this cohort is to study Saudi SLE patients for the following:

1. Understand the molecular and genetic profiles, epigenetic, immunological and microbiome alteration in relation to various SLE phenotypes in Saudi Population.
  - a. Conduct whole exome sequencing for SLE patients to identify mendilian phenotypes including novel ones by enriching sequenced patients with patients who have strong family history of the disease.
  - b. Develop a baseline Saudi polygenic risk score for our SLE patients and compare it with Caucasian risk score in order to identify novel variations among our population. In addition, trying to explore the relationship of polygenic risk score and important clinical outcomes (disease remission, disease activity, disease damage and mortality).

Identify genetic and molecular signatures. (baseline genetic, proteomic and microbiome that differentiate various SLE clinical phenotypes from one another. By doing so, we might be to better differentiate various phenotypes and understand pathological mechanism behind the difference in clinical phenotypes.

2. To assess effect of environmental, social, medication and comorbidities on SLE important disease related outcomes including disease activity and disease damage.
  - a. Examine the relationship of presence of comorbidity (in particular diabetes, HTN and dyslipidemia on disease activity, disease damage and mortality.
3. To assess molecular and genetic/epigenetic signatures of response in relation to various treatment regimens in SLE.
  - a. Identify genetic and molecular medications related signatures. (genetic, proteomic and epigenetic modifications and microbiome alteration associated with changes in disease activity states from active to remission). This will allow us to have a holistic approach to SLE pathogenesis and may take us step further toward much more personalized medicine.
4. To assess long-term important outcomes of Saudi SLE population including determinants of disease damage, recurrent hospitalization and mortality.
5. Utilize the cohort as platform for nested pragmatic clinical trials within the cohort using cohort multiple randomized controlled trial design in the near future.

The cohort will focus on addressing all these aims in context of molecular, genetic, epigenetic and mycobiome data that will be collected periodically.

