### PATIENTS RECRUITMENT AND ENROLLMENT:

Patients will be recruited from KSU-SLE specialized clinic. The clinic receive general referral from general rheumatology clinics in KSU and general referral from other clinics inside or outside KSU.

Inclusion criteria is the following:

- 1- Adult patients defined as > 18 years old.
- 2- Patients should fulfill one of the following classification criteria for SLE (ACR, SLICC or ACR/EULAR criteria).
- 3- No restriction on time of diagnosis.

Exclusion criteria:

- 1- Patients who don't fulfill classification criteria mentioned above.

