#### Disease outcomes

- Disease activity (system based from head to toe) (see standardized data collection form).
- Disease related damage.
- Cardiovascular disease (MACE), surrogate outcomes (carotid artery plaques using U.S), PAD.
- Osteoporosis (DEXA, fragility fracture (radiographic and symptomatic)).
- Malignancy.
- Renal failure requiring renal replacement therapy/renal transplant.
- Cognition (MME, MOCA)  Death/mortality.

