#### DATA COLLECTION PROCESS AND STORAGE:

Data will be collected using standardized data form (soft version is in the process of development). The form will be filled by trained individual (clinician or nurse joining the site) upon their joining of the clinical site. Training session will be conducted in standardized fashion using the glossary key for collected variables. Upon completion of data collection in each clinical visit, data will be transferred and stored in data storage program (Redcap, access or CAISIS). Data entry, cleaning, confirmation and retrieval will be handled by hired research coordinator.

Data will be collected regularly every 3 months (2-4 months). Research coordinator will ensure patients adherence to follow up protocol including attendance, data collection completion and rescheduling for missing visits.

Loss of follow up will be handled by direct communication with patients. Reasons of loss or missing follow up will be obtained using standardized data collection form through phone. Reasons include: death(reason of possible), being sick (type?), hospital admission(reason and where, records of admission should be retrieved), work, study, forgetfulness, travel, moving from city, loss of interest (due to symptoms remission, perception of poor management, follow up with another rheumatologist (why?), no specific reason).

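### Should biobank draws be tied to disease activity so that objective 3a gets active and remission samples from the same patient?

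*Protocol*

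**What the plan says.** Objective 3a in the Protocol (OBJECTIVES) seeks genetic, proteomic, epigenetic and microbiome signatures "associated with changes in disease activity states from active to remission". Objective 1 also wants signatures at baseline: "baseline genetic, proteomic and microbiome that differentiate various SLE clinical phenotypes from one another". The closing sentence of that section describes the molecular data as data "that will be collected periodically".

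On sampling, BIOLOGICAL SAMPLES AND BIOBANKING PROCESS states: "Each patient will have two comprehensive visit during which 4 heparin blood tubes will be collected from the patient for biobanking storage". It gives no period or spacing. The one event-based exception is pregnancy, with "biological sample collection at the beginning of each trimester along with postpartum sample". BUDGET AND SUPPORTING SERVICES mentions two biobank collections and four clinical collections in one sentence that ends in a per-year marker, so the two draws may be a total or a yearly number.

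Eligibility does not depend on disease stage ("No restriction on time of diagnosis") and sets no activity criterion. Activity is a recorded outcome (Disease outcomes), and the clinical schedule is by calendar: "Data will be collected regularly every 3 months (2-4 months". Samples are labelled with study number and date.

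**The concern.** A change from active disease to remission is naturally a contrast within a patient. For the layers that can change (RNA, protein, epigenetic marks, microbiome), a sample is needed in each state; germline DNA needs only one. Patients may enter in either state and no draw is triggered by activity, so whether a patient supplies a pair depends on where the calendar falls. The recorded state at each draw can be looked up afterwards, but a state that was never sampled cannot be recovered.

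A remedy seems to be at hand: activity is recorded every 3 months, a coordinator schedules visits, and pregnancy already has event-based draws. Moving one planned draw to the first visit with a changed activity state would seem to add pairs without adding tubes.

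**Working it through.** **Inputs.** From the Protocol: 40 to 50 new patients per year and visits every 3 months. Assumed, because the Protocol gives no activity rates: share active p = 0.2 to 0.5; 3-month correlation of state rho = 0.5 to 0.9; five intakes (200 to 250 patients) without attrition. There is no sample size, power or pair target to reproduce.

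**1. Two draws in total, two states.** Every patient who is not active counts as in remission. The chance of leaving the active state per 3 months is a = (1 − p)(1 − rho).

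- Second draw fixed at K visits: p(1 − p)(1 − rho^K).
- Second draw at the first changed visit, latest at K: p(1 − (1 − a)^K).

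For p = 0.3, rho = 0.7, K = 4 (12 months):

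- a = 0.7 × 0.3 = 0.21
- fixed: 0.3 × 0.7 × (1 − 0.7^4) = 0.160
- timed: 0.3 × (1 − 0.79^4) = 0.183
- ratio 1.15, or about 5 to 6 more patients with a pair out of 200 to 250 (0.0235 × 200 = 4.7; 0.0235 × 250 = 5.9)

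Over p = 0.2 to 0.5 and rho = 0.5 to 0.9 the ratio is 1.03 to 1.46 at 12 months and 1.01 to 1.17 at 6 months. The top value needs p = 0.5 and rho = 0.5.

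**2. Two draws per year.** By simulation over 1 to 5 years of follow-up, the number of patients with at least one active-then-remission pair rises by 2 to 8% against 6-monthly draws if the second draw falls no later than month 6. It rises by 12 to 17% if that draw may slip to month 9, where part of the gain comes from the longer window. Pairs also accumulate without any trigger. With shares of 0.3 active and 0.3 remission and persistence 0.3 between draws, the chance of a pair is 0.3 × 0.3 × 0.7 = 0.063 with two draws, 0.23 with four and 0.68 with ten.

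**3. Three states.** The visible text does not define active or remission, and partial improvement is a plausible intermediate state. Assume shares of 0.3 active, 0.4 intermediate and 0.3 remission. Let e be the chance of leaving the active state per 3 months (0.07 to 0.35) and d the share of those exits that go straight to remission. Remission mirrors the active state, and the intermediate state moves to each side with probability 0.75e(1 − d), which keeps the shares stable.

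- First changed visit: 0.3 × d × (1 − (1 − e)^4).
- Fixed at month 12: 0.3 × the four-step probability from active to remission.

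| d | Timed, e = 0.21 | Fixed, e = 0.21 | Ratio, e = 0.21 | Ratio, e = 0.07 to 0.35 |
|---|---|---|---|---|
| 0 | 0 | 0.035 | 0 | 0 |
| 0.2 | 0.037 | 0.050 | 0.73 | 0.67 to 0.88 |
| 0.3 | 0.055 | 0.058 | 0.95 | 0.95 to 0.98 |
| 0.4 | 0.073 | 0.066 | 1.11 | 1.03 to 1.19 |

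When d is small, the trigger spends the draw on the intermediate state. It gains only when roughly one third or more of exits go directly to remission.

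**4. Comparability.** In the two-state model, the share of timed active-then-remission pairs that close before month 12 is (1 − (1 − a)^3)/(1 − (1 − a)^4). For a = 0.21 this is 0.507/0.610 = 0.83; over the grid it is 0.77 to 0.90. Patients who stay active are sampled only at month 12. Changed and unchanged patients therefore share an interval only there, and adjustment for interval has little overlap to work with. A fixed draw gives both groups the same interval.

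**5. Recording error.** With 5 to 10% of states recorded wrongly, the 12-month gain in true, correctly recorded pairs is 0.97 to 1.43 times. At p = 0.3, rho = 0.7 and 5% error, the share of recorded pairs that are true falls from 0.81 (fixed) to 0.71 (timed). Requiring the next visit to agree gives 0.84 against 0.79.

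**The case for a change.** The best case for a change is that the timing of a tube belongs in the protocol, and no analysis plan can restore a missed state. If two draws means two in total, yields are low: with p = 0.3, at least 80% of patients give no active-then-remission pair under a fixed 12-month draw. In a model that separates remission from intermediate activity, the range is 2.4 to 25%, or about 1 to 12.5 pairs per 40 to 50 enrolled. With so small an intake, each pair counts. A sharper trigger, used only for patients sampled while active and fired only by recorded remission, avoids the weakness in step 3 and gives about 1.05 to 1.8 times the fixed yield under the three-state assumptions.

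The textual facts stand, and so does the ambiguity over the period. But low yield is not shortfall, since no number of pairs is promised. The closing sentence of OBJECTIVES and the yearly biobanking budget lean towards repeated draws, although they do not prove them, and on that reading pairs build up with follow-up. The sharper trigger would need a definition of remission that is not in the visible text, and still-active patients sampled at matched intervals. It would still leave irregular spacing for the other objectives. It would also require tubes, 24-hour DNA processing and stool kits to be ready at every 3-monthly visit, on a biobanking budget of 5,000 per year. It is a reasonable option for a later substudy, not a correction of an error.

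**Conclusion.** No change to the plan follows. It is true that no visible section ties a draw to disease activity and that the period of the two draws is unclear. The second point is missing detail that the study team can settle from its own schedule; it does not undermine an objective.

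The first is a fair trade-off. Dated calendar draws serve the baseline, phenotype and long-term objectives, keep intervals comparable between patients who change and those who do not, and allow the state at each draw to be classified afterwards. Timing a draw to any change of state gains 1.03 to 1.46 times the pairs in the most favourable simple model (two draws in total, two states, 12 months, no recording error). The gain is 2 to 8% with two draws a year and a month-6 limit, and the rule loses pairs (0 to 0.98 times) when at most 30% of exits from active disease go directly to remission. All of these figures rest on assumed activity shares and persistence, because the Protocol states none. The conclusion needs only two facts: the Protocol sets no target for pairs, and the direction of the effect depends on assumptions that the document cannot settle.

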#### CONSENT FORM AND CONSENT PROCESS:

Patients will be consented using patient centered consent form. In this process, patient will be consented by the research coordinator using standardized form (please see supplementary appendix).

Once consented, data will be collected and stored as described above.

The consent form includes three parts:

- Consenting on enrollment of observational cohort and use of data for future research.
- Consenting on collection of biological samples (serum, immunological, genetic and microbiome) for future research projects.

## BUDGET AND SUPPORTING SERVICES

Estimated cohort enrollment is 40-50 new patient/year. Each patient will have two biological data collection for biobanking and four clinical data collection/year. The budget of this prospective cohort will be divided into:

- Research coordinator. (fulltime annual salary: 72,000)
- Data management and storage program. (in collaboration with Deanship of electronic communication, KSU innovation hub and CASIS, estimated cost is 10,000)
- Biobanking (Freezer, cost of blood withdraw, tubes, serum and cells separation, cells sorting, samples storage and microbiome collection and storage. (estimated cost is 70,000/freezer, 5000/year for samples biobanking).

Upfront cost for the first year is estimated to be 150,000 Saudi riyals. Estimated annual cost is around 80,000 Saudi riyals. Multiple grant approach will be used to maintain the fund until more secure mean of fund is allocated (such as a research chair).

## NATIONAL AND INTERNATIONAL COLLABORATION

The cohort aims to be part of national and international cohorts collaborations. In setting of collaboration, only primary investigator will be included in authorship from this cohort unless other coinvestigator contributed to study in literature review, design, analysis, interpretation of the results or preparation of manuscript. Ideally, authorship should be discussed in advance among all investigators to avoid any conflict. Data sharing agreement will be required before the initiation of any collaboration in accordance to KSU-IRB standard procedure.

